6.1. Populations for Analyses

For purposes of analysis, [Table GPGK.6.1](#) defines the following analysis sets:

Table GPGK.6.1. Analysis Populations/Data Sets

Population/Data Set	Description
Screened population	All participants who sign informed consent
Randomized population	All patients who are randomly assigned a treatment arm
Modified intent-to-treat (mITT) population	All randomly assigned participants who took at least 1 dose of study drug. In the event of a treatment error, participants will be analyzed according to the treatment they were randomized.
Efficacy analysis set (EAS)	Data obtained during Study Period II from mITT, excluding patients discontinuing study drug due to inadvertent enrollment and data after initiating rescue antihyperglycemic medication or prematurely stopping study drug (last dose date + 7 days).
Full analysis set (FAS)	All available data obtained during Study Period II from mITT, excluding patients discontinuing study drug due to inadvertent enrollment, regardless of adherence to study drug or initiation of rescue antihyperglycemic medication.
Safety analysis set (SS)	All available data obtained during Study Period II or III from mITT population, regardless of adherence to study drug or initiation of new antihyperglycemic medication.

6.2. General Considerations

Statistical analysis of this study will be the responsibility of Eli Lilly and Company (Lilly) or its designee. All statistical analyses will be conducted with SAS Version 9.4 or higher unless otherwise stated. Any change to the data analysis methods described in the protocol will require an amendment ONLY if it changes a principal feature of the protocol. Any other changes to the data analysis methods described in the protocol, and the justification for making the change, will be described in the SAP or the clinical study report (CSR). Some analyses and summaries described in this analysis plan may not be conducted if not warranted by data (eg, few events to justify conducting an analysis). Listing of events will be provided in such situations. Additional analyses of the data may be conducted as deemed appropriate without further changes made to the protocol or SAP, even after the primary or final database locks (DBL).

Additionally, unless stated otherwise, statistical summaries and analyses will be conducted based on randomized maintenance dose regardless of the actual treatment received by the patient.

Unless specified otherwise, the last measurement during Visit 1 to Visit 3 (including unscheduled visits) collected prior to or on the first dose day will serve as baseline. For immunogenicity, data collected prior to the first dose time will serve as baseline. For lab and ECG, baseline needs to be prior to or within one hour after the first dose time. For patient reported outcomes, data collected at Visit 3, regardless of the timing relative to first dose, will serve as baseline.

There will be 2 estimands of interest in evaluating primary and secondary efficacy objectives. First estimand, the “efficacy” estimand, represents efficacy prior to discontinuation of study drug or initiating rescue therapy for persistent severe hyperglycemia. Analysis relative to “efficacy” estimand will be conducted using efficacy analysis set (EAS). Second estimand, the “treatment-regimen” estimand, represents the efficacy irrespective of adherence to investigational product or introduction of rescue therapy for persistent severe hyperglycemia. Analysis relative to “treatment-regimen” estimand will be conducted using full analysis set (FAS).

Unless specified otherwise, safety analyses will be conducted relative to “treatment-regimen” estimand using the safety analysis set (SS).

End of study participation for a patient will be the earliest of date of death, date of withdrawal from further participation in the study, or date of safety follow-up visit (visit 801). For patients considered to be lost to follow-up, end of study participation will be the date of lost to follow-up reported by the investigator. Patient data included in database after the last date of study participation (date of death, date of early termination, or date of safety follow-up) will be excluded from statistical analysis. Listing of such data may be provided.

Summary statistics for categorical measures (including categorized continuous measures) will include sample size, frequency, and percentages. Summary statistics for continuous measures will include sample size, mean, standard deviation (SD), median, minimum, and maximum. The summary statistics will be presented by the nominal visit.

Statistical treatment comparisons will only be performed between tirzepatide doses and placebo. Since the trials are not adequately powered to detect differences among tirzepatide doses, comparisons among tirzepatide arms will not be performed unless otherwise specified.

Statistical summaries and results of statistical analysis will be displayed in the following treatment order: 5 mg tirzepatide, 10 mg tirzepatide, 15 mg tirzepatide, and placebo.

6.3. Adjustments for Covariates

The study is stratified by country, baseline HbA1c ($\leq 8.5\%$, $>8.5\% [≤69, >69 \text{ mmol/mol}]$), and past OAM use (Yes or No). Where necessary to be included as a stratification factor, countries with fewer than 10 randomized patients will be pooled into 1 category (pooled country). For HbA1c related analyses, the pooled country and past OAM use will be used as stratification factors and baseline HbA1c as a covariate. For other efficacy analyses, the pooled country, baseline HbA1c ($\leq 8.5\%$, $>8.5\% [≤69, >69 \text{ mmol/mol}]$), and past OAM use (Yes or No) will be used as stratification factors and respective baseline value as a covariate. Stratification factors will be based on the information collected in clinical database.

6.4. Handling of Dropouts or Missing Data

For the primary and secondary efficacy endpoint analyses subject to type 1 error rate control, data for patients with missing values at the 40-week visit will be imputed based on the method described in Section 6.12.1.3. Unless specified otherwise, imputation of missing data will be limited to primary and key secondary efficacy endpoint analysis. Missing other secondary or

exploratory efficacy parameter values and missing safety laboratory values will not be explicitly imputed.

6.5. Multicenter Studies

To investigate potential regional influence on efficacy, country/pooled country will be used as a fixed factor in primary and secondary efficacy analysis.

6.6. Multiple Comparisons/Multiplicity Adjustments

Type 1 error rate control strategy for primary and key secondary efficacy objectives is illustrated in Section 6.12.3. No multiplicity adjustments will be made for conducting separate analyses relative to “efficacy” and “treatment-regimen” estimands, evaluating other secondary and exploratory efficacy objectives, and safety assessments.

6.7. Patient Disposition

Reasons for screen failure as reported by investigators will be summarized.

Listing of final study disposition and a listing of randomized treatment assignment (planned treatment) for all randomized patients will be provided. Final study disposition and study treatment disposition for all randomized patients will be summarized by planned study treatment.

6.8. Patient Characteristics

Listing of patient demographics will be provided for all randomized patients. All demographic and baseline clinical characteristics will be summarized by study treatment for all randomized patients. Baseline demographic and clinical characteristics of special interest include and not limit to: age, gender, race, ethnicity, weight, country of enrollment, HbA1c, fasting serum glucose, duration of T2DM, eGFR.

6.9. Concomitant Therapy

The prespecified concomitant medications of interest will be summarized by treatment at randomization. Additionally medications of interest initiated after randomization will be summarized. The concomitant therapies will be mapped using the World Health Organization (WHO) DRUG dictionary in the clinical trial database and will be further classified using Anatomic-Therapeutic-Chemical (ATC) codes for reporting purposes.

The concomitant medications of interest include the following groups of medication:

- baseline antihypertensive therapy, by type
- baseline lipid lowering therapy, by type
- prior use of antihyperglycemic therapy
- utilization of other antihyperglycemic therapy in Study Period II, and also in Study Period II and III
- rescue therapy due to severe persistent hyperglycemia

- initiation of following medications in Study Period II:
 - antidiarrheal medication
 - antiemetic medication

6.10. Treatment Exposure and Compliance

Listing of patients randomized but not receiving study treatment will be provided, if applicable. The listing will include patient identification, randomized treatment arm, and the reason for not receiving study treatment.

Summary of duration to end of the study (defined as time in days from date of randomization to date of safety follow-up or date of early study discontinuation) and duration on study treatment (defined as time in days from date of first dose of study treatment to date of last dose of study treatment plus 7 days) will be provided by study treatment.

6.10.1. *Exposure and Compliance to Tirzepatide*

Number of patients prematurely discontinuing study treatment prior to the 40-week visit will be provided by study treatment. Reasons for prematurely discontinuing study treatment prior to the 40-week visit will be provided by study treatment. Time-to-event analysis of premature study treatment discontinuation will be conducted.

If data warrant, proportion of patients receiving 2.5 mg, 5 mg, 7.5 mg, 10 mg, 12.5 mg or 15 mg for tirzepatide treatment groups may be presented by randomized treatment and time intervals from first dose. A listing of patients who re-initiate due to missing ≥ 3 consecutive doses may be produced.

Overall treatment compliance will be defined as taking at least 75% of the scheduled tirzepatide doses. Compliance will be calculated by taking the number of doses administered (regardless of the actual dose administered) divided by the total number of doses expected to be administered $\times 100$. Overall treatment compliance will be summarized descriptively by treatment using the mITT Population.

6.11. Important Protocol Deviations

Important protocol deviations is specified in Trial Issues Management Plan (TIMP). A listing and a summary of important protocol deviations (IPD) by treatment will be provided.

6.12. Efficacy Analysis

For the Food and Drug Administration (FDA) and potentially for other regulatory agencies, all efficacy assessments will be guided by the “treatment-regimen” estimand conducted using FAS. Assessment of the primary and secondary efficacy objectives subject to type 1 error rate control (key secondary) will be conducted with multiple imputation of missing data (see Section 6.12.1.3) at 40 weeks. Assessment of other efficacy objectives will be conducted without imputation of missing data. For publications and other purposes including some other regulatory submissions, the assessment of efficacy objectives will be guided by the “efficacy” estimand

using EAS data set without explicit imputation of missing data. A listing of patients randomized but not included in efficacy analyses (ie, not treated, discontinued treatment due to inadvertent enrollment) will be provided.

6.12.1. Primary Efficacy Analysis

The primary efficacy measure will be change in HbA1c (%) and mmol/mol) from baseline (postbaseline – baseline) to 40 weeks. Both HbA1c values as well as change from baseline in HbA1c will be summarized by treatment and nominal visit (week). When applicable, HbA1c data from local lab will be used when central lab data is not available. If scheduled HbA1c data at the primary endpoint visit is not available, unscheduled HbA1c data collected for the primary endpoint visit will be included in analysis.

6.12.1.1. Primary Analysis Relative to the Efficacy Estimand

The analysis will be conducted utilizing HbA1c data in EAS from baseline through the 40-week visit with the aid of a mixed model for repeated measures (MMRM). Restricted maximum likelihood (REML) will be used to obtain model parameter estimates and Kenward-Roger option will be used to estimate denominator degrees of freedom. The response variable of the MMRM model will be the primary measure and model terms will include treatment, visit, treatment by visit interaction, country/pooled country, and past use of OAM as fixed effects, and baseline HbA1c as a covariate. An unstructured covariance structure will be used to model the within-patient errors. If this model fails to converge, the following covariance structures will be tested in order:

- Heterogeneous Toeplitz
- Heterogeneous First Order Autoregressive
- Heterogeneous Compound Symmetry
- Toeplitz
- First Order Autoregressive
- Compound Symmetry.

The first covariance structure that converges will be used. The resulting least squares mean (LSM) estimate of mean change from baseline in HbA1c will be summarized by visit and by study treatment.

With the aid of the MMRM analysis, p-values and 2-sided 95% confidence interval (CI) for mean change in HbA1c from baseline through 40-week visit for 5 mg, 10 mg, and 15 mg tirzepatide compared to placebo will be derived and summarized.

6.12.1.2. Analysis Relative to the Treatment-Regimen Estimand

The analysis will be conducted utilizing HbA1c data in FAS at baseline and at the 40-week visit with the aid of an analysis of covariance (ANCOVA). The response variable will be the primary measure and model terms will include treatment, country/pooled country, past use of OAM as

fixed effects, and baseline HbA1c as a covariate. The ANCOVA analysis will be conducted with multiple imputation of missing primary measure (see Section 6.12.1.3 for details) and statistical inference over multiple imputation of missing data guided by Rubin (1987).

With the aid of the ANCOVA analysis, p-values and 2-sided 95% CI for mean change in HbA1c from baseline to 40-week visit for 5 mg, 10 mg, and 15 mg tirzepatide compared to placebo will be derived and summarized.

6.12.1.3. Methods for Multiple Imputations

For efficacy analysis relative to “treatment-regimen estimand,” missing HbA1c data at the 40-week visit will be imputed based on “retrieved dropouts,” defined as patients who had their HbA1c value measured at the 40-week visit in the same treatment arm who prematurely discontinued study drug. In cases where there are not enough retrieved dropouts to provide a reliable imputation model (i.e., at least 1 arm has <8 patients who discontinued study treatment early and have endpoint visit measurements, or the model implemented by the SAS program does not converge), an alternative multiple imputation method with reference to the placebo group (placebo multiple imputation) will be used. If value of the imputed HbA1c change from baseline is <-6.0% or >6.0%, that value will be set to -6.0% or 6.0%, respectively, to avoid unrealistic imputed values.

6.12.2. Secondary Efficacy Analyses Subject to Type 1 Error Rate Control

6.12.2.1. Mean Change in Body Weight and Fasting Serum Glucose From Baseline at the 40-Week Visit

The analysis for change in body weight and fasting serum glucose from baseline (postbaseline - baseline) will be conducted in a manner similar to the primary analysis in Section 6.12.1. Baseline HbA1c category ($\leq 8.5\%$, $> 8.5\%$ [≤ 69 , > 69 mmol/mol]) will be used as a fixed factor in place of baseline HbA1c as a covariate and baseline of the corresponding variable will be used as an additional covariate in the statistical model. Least squares mean estimate of mean change in body weight and fasting serum glucose from baseline will be summarized by nominal visit and by study treatment. When applicable, fasting serum glucose data from local lab will be used when central lab data is not available. For the multiple imputation of missing values, if value of the imputed weight change from baseline is <-50 kg or >50 kg, that value will be set to -50 kg or 50 kg, respectively, to avoid unrealistic imputed values; if value of the imputed fasting serum glucose change from baseline is <-20 mmol/L or > 20 mmol/L, that value will be set to -20 mmol/L or 20 mmol/L, respectively, to avoid unrealistic imputed values.

6.12.2.2. Proportion of Patients Achieving HbA1c<7% and <5.7% at the 40 Week Visit

The analysis relative to the “efficacy” estimand for the endpoint at 40 weeks will be performed using EAS with missing values imputed from an MMRM model and then dichotomized. The MMRM model includes treatment, stratification factors, visit, and treatment-by-visit interaction as fixed effects, and baseline HbA1c as a covariate. After dichotomizing continuous HbA1c, the

data is analyzed using a logistic regression model with treatment, country/pooled country, past use of OAM as fixed effects, and baseline HbA1c as a covariate. In addition, analysis will be conducted utilizing data using EAS from baseline through the 40-week visit with the aid of a longitudinal logistic regression with repeated measurements with country/pooled country, past use of OAM, treatment, visit, treatment-by-visit interaction as fixed effects, and baseline HbA1c as a covariate. In case longitudinal logistic model does not converge due to small number of events, logistic regression will be utilized to analyze proportion of patients achieving HbA1c<7% at nominal visits.

Analysis relative to “treatment-regimen” estimand will be conducted by utilizing HbA1c data in FAS at baseline and at the 40-week visit with the aid of a logistic regression with multiple imputation of missing HbA1c data at the 40-week visit (see Section 6.12.1.3 for details). Model terms will include treatment, country/pooled country, past use of OAM as fixed effects, and baseline HbA1c as a covariate and statistical inference over multiple imputations will be guided by Rubin (1987).

Similar analyses will be performed for proportion of patients achieving HbA1c <5.7%.

6.12.3. Type 1 Error Rate Control Strategy for Primary and Key Secondary Efficacy Analysis

Since they are intended for different purposes, no type 1 error rate adjustments will be made for conducting analysis relative to “efficacy” and “treatment-regimen” estimands. For analysis within each estimand, type 1 error rate control strategy for evaluation of primary and key secondary objectives is illustrated in [Figure GPGK.6.1](#). The type I error rate control strategy for the Pharmaceuticals and Medical Devices Agency (PMDA) is in [Appendix 1](#).

The primary and key secondary objective hypotheses are as follows,

- $H_{5,1}, H_{10,1}$, and $H_{15,1}$: Superiority test of tirzepatide 5 mg, 10 mg, 15 mg versus placebo in HbA1c change from baseline at 40 weeks respectively.
- $H_{5,2}, H_{10,2}$, and $H_{15,2}$: Superiority test of tirzepatide 5 mg, 10 mg, 15 mg versus placebo in body weight change from baseline at 40 weeks respectively.
- $H_{5,3}, H_{10,3}$, and $H_{15,3}$: Superiority test of tirzepatide 5 mg, 10 mg, 15 mg versus placebo in proportion of patients achieve HbA1c<7% at 40 weeks respectively.
- $H_{5,4}, H_{10,4}$, and $H_{15,4}$: Superiority test of tirzepatide 5 mg, 10 mg, 15 mg versus placebo in fasting serum glucose (FSG) change from baseline at 40 weeks respectively.
- $H_{5,5}, H_{10,5}$, and $H_{15,5}$: Superiority test of tirzepatide 5 mg, 10 mg, 15 mg versus placebo in proportion of patients achieve HbA1c<5.7% at 40 weeks respectively.

$H_{5,1}$, $H_{10,1}$, and $H_{15,1}$ will be initially tested each at 0.01667 significance level. A graphical testing scheme (Bretz et al. 2009, 2011) presented in [Figure GPGK.6.1](#) will be used to strongly control for type 1 error.

[figure not shown]

Figure GPGK.6.1. Type 1 error control strategy for primary and key secondary efficacy endpoints.

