Since they are intended for different purposes, each of the 2 primary efficacy assessments relative to efficacy and treatment regimen estimands will be conducted at a family-wise type 1 error rate of 0.05. Additional details, including analysis methods for key secondary endpoints and a strategy for controlling the overall family-wise type 1 error rate at an alpha of 0.05 for primary and key secondary endpoint evaluation will be provided in the SAP.

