10.3.3.2. Secondary Analyses

The secondary study objectives subject to type 1 error rate control are as follows:

- Superiority of tirzepatide dose(s) to placebo relative to mean change in body weight from baseline to the 40-week visit
- Superiority of tirzepatide dose(s) to placebo relative to proportion of patients achieving the target value of HbA1c <7% (<53 mmol/mol) at the 40-week visit
- Superiority of tirzepatide dose(s) to placebo relative to mean change in FSG (central laboratory) at the 40-week visit
- Superiority of tirzepatide dose(s) to placebo relative to proportion of patients achieving the target value of HbA1c <5.7% (<39 mmol/mol) at the 40-week visit

The type 1 error-controlled strategy for the primary and secondary endpoints will be described in the SAP. All type I error-controlled secondary efficacy analyses will be conducted relative to both estimands, the “efficacy” estimand and the “treatment-regimen” estimand separately.

Analysis of change from baseline in body weight and FSG at the 40-week visit will be conducted in a manner similar to the primary efficacy analyses with baseline HbA1C category [$\leq 8.5\%$ (≤ 69 mmol/mol) or $>8.5\%$ (>69 mmol/mol)] added in the model, and baseline of the corresponding variable as a covariate. The MMRM analyses were described in Section 10.3.1.

Comparisons among treatments relative to the proportion of patients achieving the HbA1c target value of <7.0% (<53 mmol/mol) and <5.7% (<39 mmol/mol) at the 40-week visit will be conducted using a logistic regression analysis with terms: treatment, country, and baseline HbA1c as a covariate. In the analysis of patients achieving the HbA1c target value relative to the “efficacy” estimand, patients with missing values at the 40-week visit will be excluded. In the analysis of patients achieving the HbA1c target value relative to the “treatment-regimen” estimand, missing values at the 40-week visit will be imputed based on observed data at respective visits from patients in the same treatment group who had their efficacy assessed after early discontinuation of study drug and/or initiation of rescue medication. The analysis will be conducted with multiple imputations and statistical inference over multiple imputations will be guided by the method proposed by Rubin (1987).

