6.13.3. Vital Signs	30
6.13.4. Electrocardiograms	31
6.13.5. Clinical Laboratory Evaluation	31
6.13.6. Immunogenicity	32
6.14. Health Outcomes	32
6.14.1. EQ-5D-5L	32
6.14.2. Impact of Weight on Self-Perceptions Questionnaire	33
6.14.3. Ability to Perform Physical Activities of Daily Living	33
6.15. Subgroup Analyses	33
6.15.1. Subgroup Analysis of HbA1c Change at 40 Weeks	33
6.15.2. Subgroup Analysis of Weight Change at 40 Weeks	33
6.16. Interim Analyses and Data Monitoring Committee	34
6.17. COVID-19 Impact Assessment	34
6.17.1. Patients Impacted by COVID-19	34
6.17.2. Adverse Events	34
6.17.3. Patient Disposition	34
6.17.4. Study Visits	34
6.17.5. Mitigation Summary	34
6.17.6. Measures Related to Primary and Key Secondary Objectives	34
7. Unblinding Plan	35
8. References	36
9. Appendices	37

Table of Contents

Table		Page
Table GPGK.6.1.	Analysis Populations/Data Sets.....	13
Table GPGK.6.2.	Secondary and Exploratory Efficacy Analyses not Controlled for Type I Error.....	21
Table GPGK.6.3.	Definitions of Hypoglycemic Event Categories	25
Table GPGK.6.4.	Categorical Criteria for Abnormal Blood Pressure and Pulse Measurements.....	30
Table GPGK.6.5.	Selected Categorical Limits for ECG Data.....	31

Table of Contents

Figure		Page
Figure GPGK.5.1.	Illustration of study design for Clinical Protocol I8F-MC-GPGK.....	11
Figure GPGK.6.1.	Type 1 error control strategy for primary and key secondary efficacy endpoints.....	20

Table of Contents

Appendix		Page
Appendix 1.	Statistical Analysis for Japan	38
Appendix 2.	Searching Criteria for Adverse Events of Special Interest (AESI)	39

3. Revision History

Statistical Analysis Plan (SAP) Version 1 was approved prior to the first patient receiving study drug.

The second version was approved before the final database lock. The following represent major changes made for the second version:

1. Update definition of analysis set. Per agreement with the US FDA, exclude patients discontinuing study drug due to inadvertent enrollment from efficacy analyses.
2. Update baseline definition for selected measures to minimize missing values at baseline.
3. Update the language to handle lack of convergence in longitudinal logistic regression analysis due to low number of events for hemoglobin A1c (HbA1c) and weight loss target analyses.
4. Remove subgroup analyses for adverse events due to low incidence.
5. Add section to assess SARS-CoV-2 (COVID-19) impact.

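### The efficacy-estimand analysis of HbA1c <7% and <5.7% imputes from an MMRM with no draws or pooling stated, and SAP 6.12 says this estimand uses no explicit imputation

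*SAP*

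**What the plan says.** HbA1c <7% and <5.7% at Week 40 are key secondary endpoints under type 1 error control (SAP 4.2; hypotheses H5,3 to H15,3 and H5,5 to H15,5 in SAP 6.12.3). The documents handle missing Week-40 values for the efficacy estimand in three ways:

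- SAP 6.12.2.2: the analysis is "performed using EAS with missing values imputed from an MMRM model and then dichotomized"; after that the "data is analyzed using a logistic regression model with treatment" and the usual covariates. A longitudinal logistic regression is added, without saying which of the two decides the hypotheses.
- SAP 6.12: the efficacy estimand is assessed "using EAS data set without explicit imputation of missing data".
- Protocol 10.3.3.2: for this estimand, "patients with missing values at the 40-week visit will be excluded".

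The next paragraph of SAP 6.12.2.2, on the treatment-regimen estimand, does specify multiple imputation and says that "statistical inference over multiple imputations will be guided by Rubin (1987"). Nothing equivalent appears for the efficacy estimand.

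**The concern.** The efficacy analysis set drops data after rescue or after early stopping of study drug (SAP 6.1), so every such patient lacks a usable Week-40 value. The text of 6.12.2.2 leads to one completed data set and one logistic fit, in which an imputed responder counts exactly like an observed one. The standard error then ignores the uncertainty of the imputation. If the imputed value is the model's predicted mean, it also lacks residual scatter, so dichotomising it moves patients to the side of the cut-off where their mean already lies.

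Two programmers could both follow the section and report different odds ratios and intervals. SAP 6.12 makes this estimand the basis for publications and some other submissions, so those reported results are exposed.

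**Working it through.** **Inputs from Protocol 10.1.** 118 patients per arm, SD 1.1, effect 0.65%, and rescue or discontinuation of up to 25% (tirzepatide) and 35% (placebo). The plan's own power figure reproduces: 118 × 0.75 = 88.5 and 118 × 0.65 = 76.7 patients; SE = 1.1 × √(1/88.5 + 1/76.7) = 0.172; 0.65/0.172 = 3.79; less 2.387 (two-sided 0.017) leaves 1.40, so power is 91.9%, in line with the stated 90% or more. It concerns mean HbA1c and does not depend on this point. The documents give no figure for the responder analyses.

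**How many patients.** At the ceilings, 118 × 0.25 = 29.5 patients per tirzepatide arm and 118 × 0.35 = 41.3 placebo patients need an imputed status.

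**Predicted means.** Assume a Week-40 mean of 8.0. The true share below 7.0 is Φ((7.0 − 8.0)/1.1) = 18.2%. If the imputation model explains half the variance, predicted means have SD 1.1 × √0.5 = 0.778, and only Φ(−1/0.778) = 9.9% fall below 7.0. At a mean of 6.0 the error reverses: 81.8% true, 90.1% predicted.

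**One unpooled draw.** Two-arm check: 118 per arm, 35%/25% missing at random, both means 7.35, half the variance explained, Wald interval for the difference in rates. The average reported SE was 0.0626 and the actual spread 0.0721, a ratio of 0.868. Implied coverage is 2Φ(1.96 × 0.868) − 1, about 91%; the simulated value was 90.2%. With 20 imputations pooled by Rubin's rules it was 95.6%.

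**Simulation closer to the plan.** Four arms of 118, eight post-baseline visits, SD of change 1.1, logistic model with treatment and baseline, 3,000 trials per scenario. Assumed, because the documents do not give them: baseline mean 8.0 and SD 0.7 truncated to 7.0–9.5; baseline slope on change −0.3; effect and placebo change reaching full size at Week 20; placebo change 0 or −0.5; residual correlation 0.70 to 0.85 per 8 weeks; monotone loss, completely at random or dependent on observed HbA1c. Country and past oral medication use were left out. Results for <7%, effect 0.65%:

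| Missing (placebo/tirzepatide) | Method | Error in odds ratio | 95% interval coverage |
|---|---|---|---|
| 35%/25% | predicted means | +13% to +43% | 72% to 93% |
| 35%/25% | one unpooled draw | within 3% | 90% to 94% |
| 35%/25% | 20 imputations, pooled | within 3% | 96% to 98% |
| 35%/25% | exclusion | −8% to +2% | 94% to 96% |
| 35%/25% | longitudinal logistic | −6% to +2% | 94% to 96% |
| 25%/16% | predicted means | +8% to +24% | 90% to 95% |
| 25%/16% | one unpooled draw | – | 92% to 94% |
| 15%/8% | predicted means | +5% to +15% | 93% to 95% |
| 15%/8% | one unpooled draw | – | 94% to 95% |

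A separate simulation at 35%/25% gave +15% to +25% and 87% to 93% coverage for predicted means, 91% to 93% for one draw, and an odds ratio within 3% with 97% to 98% coverage when pooled.

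**One scenario in rates** (placebo/tirzepatide). Complete data: 18.2%/36.4%, crude odds ratio (0.364/0.636)/(0.182/0.818) = 2.57. Predicted means: 15.3%/34.4%, odds ratio 2.90, 13% higher. Pooled: 18.0%/36.3%, odds ratio 2.60. The differences in rates are 18.3, 19.2 and 18.3 points; exclusion gives 19.8.

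**<5.7%** (effect 1.5%, placebo change −0.5). Predicted means show about 36% instead of 38% on tirzepatide and 3.6% to 4.5% instead of 5.4% on placebo; coverage stays at 96%.

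**The case against.** The strongest reply is that the SAP is silent, not wrong. It never says single or deterministic imputation, and multiple imputation may have been intended. That stands: a reader might infer that predicted means are prescribed, and the text does not support it. The large odds-ratio bias needs both that reading and missingness near a ceiling the protocol words as an upper limit. It does not remove the point, because the single unpooled draw is also too narrow at that ceiling, and the contrast with the adjoining paragraph leaves pooling unstated exactly where it is needed.

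Other replies stand as limits:

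- The difference in rates is not overstated in general. At an assumed baseline mean of 8.5 instead of 8.0, checks put the distortion between about −0.5 and +0.5 points.
- A reader might infer inflated family-wise error. The three HbA1c-change tests start with 3 × 0.01667 = 0.05, the whole alpha, so the responder tests are reached only after a primary rejection. With no treatment effect, the <7% test rejected at 0.01667 together with the same dose's primary test in 0.3% to 1.3% of trials (predicted means) and 0.3% to 1.0% (one draw), all below 1.67%.
- Replacing the protocol's exclusion rule is not itself a fault. The protocol leaves further details to the SAP, "including analysis methods for key secondary endpoints", and SAP 6.2 lets the reason appear later: "the justification for making the change, will be described in the SAP or the clinical study report (CSR"). The revision history, which mentions responder analyses only to "handle lack of convergence in longitudinal logistic regression analysis due to low number of events", records changes between SAP versions, so its silence on the protocol rule proves nothing.
- The general pointer in SAP 6.4 is bounded by 6.12.1.3, which covers only the treatment-regimen estimand. That, and whether the other responder endpoints in Table GPGK.6.2 are imputed, is tidying.
- The longitudinal logistic regression is a sound cross-check already in the plan.

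**Conclusion.** The point holds as an unspecified method plus a direct contradiction between SAP 6.12.2.2 and 6.12, and should be fixed. The textual finding is firm; its size is conditional. At 35%/25% missing, under the assumed HbA1c parameters and with loss at random given observed data, a single unpooled draw leaves <7% intervals too narrow (coverage about 90% to 94%). Predicted means would also overstate the <7% odds ratio, by roughly 13% to 43% in one set of scenarios and 15% to 25% in another. At 15%/8% missing the harm is small: coverage is 93% to 95% even with predicted means, although the odds ratio would still be 5% to 15% high.

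The documents do not support going further. No family-wise error inflation, under-coverage for <5.7% or general bias in the rate difference is claimed. The FDA analysis uses the treatment-regimen estimand with pooling, and the PMDA error-controlled family (SAP Appendix 1) covers only HbA1c change and body weight, so neither is affected.

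**What to change.** In SAP 6.12.2.2, state for the efficacy estimand that missing Week-40 HbA1c in the efficacy analysis set is multiply imputed from the MMRM predictive distribution, with parameter and residual draws and a stated number of imputations; that each completed data set is dichotomised and analysed by the logistic model; and that results are pooled with Rubin's rules. Name this as the deciding analysis for H5,3 to H15,3 and H5,5 to H15,5, with the longitudinal logistic regression as supportive. Add this exception to the sentence in SAP 6.12 that rules out explicit imputation.

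The cost is SAP wording and modest programming, since pooling is already planned for the other estimand. Intervals become wider and slightly conservative. In the simulation at 35%/25% missing, power at 0.01667 for a 0.65% effect was 66% to 83% pooled, against 78% to 87% with one unpooled draw, 80% to 88% with complete data, and 61% to 71% with exclusion or the longitudinal model.
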